4.3 Aim 3 Methods (Implementation)

Implementation is being guided by the Consolidated Framework for Implementation Research (CFIR), which serves as the project's conceptual framework. We will use a mixed methods approach to evaluate implementation. Based on data from sites visits, observations made during Kick-Offs and collaborative telephone calls, and interviews at 6-months and 12-months after active implementation, we will assess: the number of improvement initiatives completed; the level of team organization for providing and improving TIA care; the degree to which sites engage in ongoing reflecting and evaluating, goal setting, and planning; participation in the monthly collaborative calls; the local adoption and adaptability of the program over the course of the study; and contextual factors to identify optimal context associated with implementation success. The two primary implementation outcomes will be the number of implementation activities completed and the level of team organization [GO Score] for providing and improving TIA care.

Implementation Outcome	Domain	Measurement
Implementation Activities		
• Kick-Off plans & plan updates on Hub• Collaborative call updates – action plans and FAST• Interviews at 6- and 12-months• Facilitator tracking sheet and updates
Team activation	Overall team activation	
• GO score based on interview data, reports from sites (e.g., emails), and updates from monthly collaborative calls, facilitator tracking sheet

		
 • Kick-Off participation
	Audit and feedback	
 • Hub usage—data pages; user interviews • Interviews at 6 and 12 months • Relevant discussion from Collaborative Calls captured on FAST • Facilitator notes and tracking sheet
	Reflecting and evaluating	
 • Meeting as a team to discuss data: obtained from updates during monthly calls captured on FAST and 6 & 12-month interviews • Facilitator notes and tracking sheet
	Planning	
 • Hub usage—planning tool • 6 & 12-month Interview questions and any relevant input from Collaborative Calls captured on FAST. • Facilitator notes and tracking sheet
	Goal setting	
 • Obtained from 6 and 12 month interviews • Kick off WF goal • Any relevant discussion from Collaborative Calls and on FAST template • Facilitator tracking sheet and notes
External facilitation		
 • Dose, Temporality, Target: Tracking sheet
Community of practice		
 • Participation in monthly calls • Posting projects and other locally developed resources on the hub • Presenting on collaborative calls or SQUINT calls • Sharing/discussing best practices with other facilities outside of collaborative calls [6 and 12-month interviews; Facilitator notes and tracking sheet
Cosmopolitanism		
Local adaptation		
 • A site-specific PREVENT program description of adopted elements developed based on updates during monthly calls and this will be reviewed during interview with sites after active implementation. Adaptation based upon program contents, settings, temporality, and roles.
Peer pressure		
 • Evaluated during debriefs from Kick-Offs and after monthly conference calls and at the end of active implementation interviews • FAST template recording from calls
Clinical champion		
 • CHAMP measure at baseline and end of active implementation interviews
Culture		
 • OCAI measured at baseline and end of active implementation interviews

GO Score – Group Organization Score²² for Providing and Improving TIA Care is a measure of team activation on a 1-10 scale for either improving or providing TIA Care based on specified provider practices sustained at a given time period. A score between 1-3 denotes a beginning level with no facility wide approach. A score between 4-5 reflects a developing approach. A score of 6-7 denotes a basic proficiency and a score of 8 indicates an intermediate proficiency. Finally, a score of 9-10 reflects a TIA system that is implemented facility wide and can sustain key personnel turnover.

FAST – Fast Analysis & Synthesis Template. This template serves as a rapid, systematic method for extracting key concepts across data sources and is derived from A. Hamilton methodology²³ and used most recently to summarize qualitative findings across regions (HSRD Summer 2017 featured presentation). In a similar manner, we will utilize the FAST template to capture key concepts from the Collaborative Calls, Stakeholder interviews, and other data sources in a condensed manner that accords with interview guides.

Aim 3 Primary Implementation Analysis

As described above, interviews will be audio-recorded. Audio recordings will be transcribed verbatim and transcripts will be de-identified and imported into an Nvivo11 project file for data coding and analysis. Project team members will independently read and coded identical transcripts using a common codebook derived from the semi-structured interview guide. Each coded transcript will be merged into a single file, and the project team will meet as a group to review and discuss similarities and differences in the coding selections until a shared understanding of each item in the codebook had been developed.

In addition to qualitative coding, the analysis team will directly apply implementation science constructs to the qualitative data. Individual members of the analysis team will rate interview transcripts first for construct and valence (i.e., positive, neutral or negative).^{24,25} When all the interviews in a site visit have been rated, the analysis team will review those ratings and then score each VAMC with a facility-level valence (i.e., positive, neutral, or negative) for the key implementation strategies and CFIR constructs: reflecting and evaluating, goal setting and feedback, planning, and champions.²⁴⁻²⁶

CFIR. From the 5 CFIR Domains, we are interested in the local implementation of the novel Intervention domain within the Inner Setting, i.e., each of the VAMCs. Within the Implementation Processes domain, we are interested in the clinical provider self-efficacy (Individual Domain) to implement PREVENT and to perform the 7 clinical processes upon which the without fail rate is calculated, and the organization's cosmopolitanism (External Setting), the degree to which an organization is networked with other external organizations. The table below offers examples of how the CFIR construct for "Champions" has been coded, rated, and scored.

Example of Valence Ratings.

Champions (Process)		Definition: Individuals who dedicate themselves to supporting, marketing, and driving through an implementation, overcoming indifference or resistance that the intervention may provoke in an organization.		
	Positive	Neutral	Negative	
Examples	
• Presence of multiple champions in different disciplines that communicate regularly• Individuals that don't take "No" for answer; constantly talk to others about stroke• Clinicians with deep, sustained interest in ACS	
• Potential stroke champions have been identified, but impact is limited/limited• Respondents identify champions but in ambiguous or neutral manner.	
• The absence of champions has a detrimental effect on ACS• Individuals may be having negative roles or stymying improvement efforts• "Anti"-champions exist	
Sample Quotes	My motto is that if the rules weren't made to be broken,	We were hoping to get sort of a champion,	I will fault my own leadership as being lacking. this was	

they're made to be bent, and I certainly bend a lot of them. (1000SV2, +2)
 
Wherever I am, I'm talking about stroke. If I'm in the beauty shop and saying, 'Hey you know the warning signs of stroke?' (900SV2, +2)
 
We have a team of stroke champions, multidisciplinary, most of which originated from the workgroup that developed the care path. We meet weekly to run through our stroke patients for that week and kind of do Multidisciplinary Team rounds, but then also just to talk about any issues that arise. (200SV3, +2)
	
someone who would gather statistics and give feedback on a real timely basis when we do get patients who are admitted with stroke to see whether they received TPA, and if not, why not and answer questions like that. (700SV3, 0)
 
I guess [Stroke Director], I would see her as the closest to that. I guess just because she has been our point of contact and she does seem to have a real vested interest in making sure the process runs smoothly. (700SV1, 0)
	
just an added responsibility. It wasn't like, you're going to get some support or some time to work on this stuff. I understand that resources are limited, but if you want a five-star meal you can't shop at Aldi, right? You've got to have some - you've got to spend some money and get some good ingredients. (500SV1, -2)
 
Part of the problem has been there has been a lot of bad blood between the administration and [CHIEF OF NEUROLOGY]. It's personal sort of rift. So in a sense, I don't really like you, I'm not really going to support your stuff. (1100SV2, -2)

--	--	--

DOMAIN: INTERVENTION

Complexity	Perceived difficulty of implementation, reflected by duration, scope, radicalness, disruptiveness, centrality, and intricacy and number of steps required to implement.
Design Quality & Packaging	Perceived excellence in how the intervention is bundled, presented, and assembled as noted from the staff evaluations.
Usability	Perceived degree of usefulness to the development and implementation of the local PREVENT program

DOMAIN: INNER SETTING – Local context

Construct	Short Description
Structural Characteristics	The social architecture, age, maturity, and size of an organization.
Networks & Communications	The nature and quality of webs of social networks and the nature and quality of formal and informal communications within an organization.
Culture	Norms, values, and basic assumptions of a given organization.

Goals & Feedback	The degree to which goals are clearly communicated, acted upon, and fed back to staff, and alignment of that feedback with goals.
Learning Climate	A climate in which: a) leaders express their own fallibility and need for team members' assistance and input; b) team members feel that they are essential, valued, and knowledgeable partners in the change process; c) individuals feel psychologically safe to try new methods; and d) there is sufficient time and space for reflective thinking and evaluation.
Leadership Engagement	Commitment, involvement, and accountability of leaders and managers with the implementation.
Available Resources	The level of resources dedicated for implementation and on-going operations, including money, training, education, physical space, and time.

DOMAIN: IMPLEMENTATION PROCESS

Construct	Short Description
Planning	The degree to which a scheme or method of behavior and tasks for implementing an intervention are developed in advance, and the quality of those schemes or methods.
Champions	Individuals who dedicate themselves to supporting, marketing, and 'driving through' an implementation, overcoming indifference or resistance that the intervention may provoke in an organization.
Reflecting & Evaluating	Quantitative and qualitative feedback about the progress and quality of implementation accompanied with regular personal and team debriefing about progress and experience.

Domain: INDIVIDUAL

Self-efficacy	One's believe in their ability to perform a specific behavior
----------------------	---

Categorical data captured by the analysis team will include individual-level data (e.g., job position, primary clinical area, etc.) for each of the interviews. We will use NVivo11 to integrate the tagged qualitative data, the scored construct data, the standardized survey data (e.g., OCAL measure), the categorical data, and the quantitative outcome data in a single, unified project file with multiple codebooks (qualitative, scored constructs, quantitative, categorical). We will use the NVivo11 "matrix query" feature to explore relationships between the qualitative, construct, quantitative and categorical data, and through this direct cross-referencing of qualitative and

quantitative data iteratively analyze how specific combinations of intervention components, implementation strategies and features of local context influence project outcomes.

Aim 3 Hypothesis A: that sites that engage in ongoing reflecting and evaluating, goal setting, and planning will realize the greatest implementation success (based on the number of implementation activities completed and the level of team organization for providing and improving TIA care at 12 months).

As described above, the degree to which sites engage in reflecting and evaluating, goal setting, and planning will be assessed using an approach to qualitative coding of CFIR constructs that assigns valence and in this way each site will be assigned a designation that varies from -2 to +2 for the four constructs ((a) reflecting and evaluating, (b) goal setting, (c) planning, and (d) champions). The level of team organization is based on the GO score which varies from 1 (least complex level of organization) to 10 (most complex level of organization).

Example Table: Aim 3A

Site	Final Construct Score (possible range: -2 to +2)			PRIMARY IMPLEMENTATION OUTCOMES	
	Reflecting and Evaluating	Goal Setting	Planning	Number of Improvement Initiatives Completed	Final GO Score
A					
B					
C					
D					
E					
F					

Aim 3 Hypothesis B: that sites with greatest implementation success (based on the number of implementation activities completed and the level of team organization for providing and improving TIA care at 12 months) will achieve the highest Without-Fail rate. The measures of implementation success will be included in the GLMM model described above as cluster-level (aka facility-level) covariates. Specifically, the change in GO score from baseline to post-implementation as well as the number of implementation activities during the active implementation phase will be included in the model along with the covariate of the number of collaborative calls attended.

Example Table: Aim 3B

Site	PRIMARY IMPLEMENTATION OUTCOMES				Final Without-Fail Rate
	Number of Implementation Activities Completed	Number of Collaborative Calls Attended	Final GO Score Provide	Final Go Score Improve	
A					
B					
C					
D					

E					
F					

Aim 3 Secondary Implementation Analyses

Example Table: Aim 3C

Strategies Used	Final Without Fail Rate	
	High	Low
Reflecting (+/-)		
Goal Setting (+/-)		
Planning (+/-)		
Facilitation Dose		
Collaborative Calls (Dose)		
Use of Hub (Data Pages)		
Clinical Champion (scale rating)		
OCAI organizational profiles		

Identification of Effective Implementation Strategies

As described above, PREVENT employs three primary implementation strategies: (1) team activation via (a) audit and feedback, (b) reflecting and evaluating, (c) planning, and (d) goal setting; (2) external facilitation; and (3) building a community of practice. In addition, PREVENT allows for local adaptation of the intervention and also takes advantage of peer pressure. The identification of successful implementation strategies will be based on a mixed methods assessment where the change in the Without-Fail rate will be used to define implementation success. As shown in Table 3C, we will compare facilities based upon a High Final Without Fail rate as defined as 50% or higher compared to those defined as low final rate (less than 50%) by the degree of engagement in implementation strategies and dose received as well as strength of clinical champion and organizational culture. Similarly, we will compare the rate of change [% of change] from baseline to end of active implementation.

External Facilitation

We will describe the dose, type, and temporal trends in external facilitation that is provided to each of the sites over the course of the one-year active implementation period. We will also ask participants to describe their experience with and their assessment of the external facilitation that was provided by the PREVENT program staff during the interviews at 6-months and 12-months post-implementation.

Community of Practice: Collaborative Call Assessment

Given that a key component of the implementation plan was the development of a virtual collaborative via monthly conference calls, we are particularly interested in the perceived value of the collaborative calls.

As part of the interviews at 6-months and 12-months post-implementation we will code the interviews to elicit the following emerging topics based upon the program element evaluation and motivation questions:

- Did the calls increase your utilization of the hub?
- Did the calls create a sense of profession community?

- Did the calls serve to maintain your interest and enthusiasm about TIA quality improvement?
- What was the single most important element of PREVENT participation for you working in your facility: kickoff, monthly process data on the hub, having access to the PREVENT community, the monthly calls, the library of resources and materials on the hub?

As part of the secondary implementation analysis we will examine whether participation in the calls (number of participants per site per call and presenting on the calls) relate to the Go Score. We will also examine whether hub usage (by date) increased just prior to or immediately following the calls. Similarly, we will examine whether email contact with the PREVENT team increased just prior to or immediately following a collaborative call. Finally, we will describe the “eureka moments” that occurred during or as a result of the calls.

Use of the HUB

Qualitative interview data from 6 months post-implementation and 1-year post-implementation will be used to understand how sites used the hub for data review and project planning. We will also identify whether and how the resources included in the hub library were used.

We will also examine data collected by the hub itself to identify the pages that are most commonly visited. Moreover, we will interview key users from each site with in depth usability questions.

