4.2 Aim 2 Methods (Effectiveness)

Design

This five-year stepped-wedge^{20,21} evaluation includes a total of 6 sites, where active implementation is initiated in 3 waves each of which includes 2 sites. The project involves three

[figure not shown]
phases at each of the six sites: a one year-baseline phase, a one-year active implementation phase, and a sustainability phase of at least one year in duration follows the end of active implementation.

Power and Sample Size

The six site, stepped wedge design provides >90% power to detect an improvement in the mean facility Without-Fail rate from 25% during the baseline data period to >50% during the active implementation data period. The goal for the sample size was to recruit sites with at least 50 TIA patients per year, however, power was preserved with at least 30 TIA patients per year.

The figures below provide the plots of the power calculated based on the modified formula for testing the intervention effect $H_0: \theta = 0, H_1: \theta = \theta^M$ for the intervention effect size θ^M ranging from 0.1 to 0.3 when taking account for a potential decrement in intervention effect over time γ . The plot was based on a total of 6 clusters with a cluster sample size of 30, 50 and 70, respectively. The results demonstrated that this variant of SWD generally has a reasonable power (greater than or equal to 0.90) for detecting the intervention effect when the effect size is at least 0.15 with a cluster size no less than 30. The coefficient of variation (CV) was set at 0.2, 0.4, 0.6, and 0.8 to cover a wide range of the between-hospital variation. The CV seemed to have little effect on power.

Site Selection

Sites were invited to participate on the basis the basis of demonstrated gaps in quality of care (identified using the validated eQMs). Specifically, sites were invited to participate if they had baseline without-fail rates of <50%. Invitations were sent via email to higher volume sites first and recruitment continued until 6 participating sites were identified. No minimum threshold on volume was employed because our goal was to include sites which were diverse so that the results might be widely generalizable across the full spectrum of VHA facilities.

Allocation of Sites to Waves

Although some stepped-wedge trials randomly assign facilities to waves, PREVENT sites were allocated to waves on the basis of the pragmatics of the ability to schedule baseline and Kick-Off meetings.

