where i indexes the site ($i = 1, 2, 3, 4, 5, 6$); j the implementation phase (1: baseline period; 2: active implementation phase; 3: one year after the active implementation phase); k the encounter at the i^{th} site and the j^{th} phase ($k = 1, 2, \dots, n_{ij}$); n_{ij} is the total number of encounters at the i^{th} site and the j^{th} phase; $X_{ij,k}$ and $Z_{ij,k}$ the indicators of the active implementation phase and one year after the active implementation phase, respectively; $W_{ij,k}$ the vector of the k^{th} encounter's characteristics at the i^{th} site and the j^{th} phase that could include the site characteristics; $Y_{ij,k} = 1$ the indicator of observation of “Without-Fail” care process on the k^{th} encounter at the i^{th} site and the j^{th} phase. For this model, μ represents the average log odds of Without-Fail care across the 6 sites at baseline; θ the log odds ratio between the active implementation phase and the baseline indicating the intervention effect during the active implementation phase; and γ the log odds ratio between one year after the active implementation phase and the baseline indicating the intervention sustainability effect post the implementation; α_i and β_j are the site and phase specific random effects that are assumed to be multivariate normal. After fitting the model, the normal theory can be applied to test the intervention effect at the active implementation phase and the intervention sustainability effect.

Secondary Aim 2 Analyses: Several secondary effectiveness analyses are planned.

Comparison to Matched Controls

Six control sites will be matched to each of the six PREVENT active implementation sites on the basis of: TIA patient volume, facility complexity (i.e., teaching status, intensive care unit level), and quality of care (measured by the without-fail rate). The total number of control sites will be 36. The definition of the baseline period (the specific start and end dates of the one-year baseline period) for each matched control site will be identical to the definition used for the PREVENT active site to which the controls are matched. We will compare changes in quality and outcomes at control sites to changes at PREVENT sites as a method for assessing temporal trends.

Changes in Individual Processes of Care

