4.4 Secondary Aim Methods (Sustainability)

The sustainability analysis will include: a comparison of the change in the Without-Rail rate from the baseline data period to the sustainability period (blue versus pink shading above). We will build multilevel models as described above for the Aim 2 analysis as described above.

We will explore whether sites with the greatest use of their own quality data (e.g., did they generate their own data, the frequency with which they reviewed the process of care data on the hub, whether they incorporated process of care data into routine work flow, did they conduct their own chart reviews) demonstrate the greatest program sustainability. Again, these cluster-level characteristics will be included in the GLMM model described above.

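### The Hypothesis B model in Aim 3, read plainly, pools three site-level implementation measures over baseline and later phases, and states no small-sample method for six sites

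*Combined protocol and SAP*

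**What the plan says.** Hypothesis B (Section 4.3) expects the sites with the greatest implementation success to reach the highest Without-Fail rate. Its example table lists the final rate for each site. The method is: "The measures of implementation success will be included in the GLMM model described above as cluster-level (aka facility-level) covariates". Two measures are named, the change in GO score from baseline and the number of activities in the active phase, and these "will be included in the model along with the covariate of the number of collaborative calls attended".

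The model referred to is the logistic mixed model under Primary Aim 2 Analysis (Section 4.2). Its terms are an intercept, random site and phase effects, an active-phase indicator (coefficient theta), an indicator for the year after (gamma), and an additive covariate term W with coefficient tau. It covers encounters from baseline, active implementation and the year after. The SAP states no product of W with the phase indicators, no site-by-phase random effect, no restriction to later encounters and no small-sample correction.

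On inference, the SAP says "the normal theory can be applied to test the intervention effect". That sentence goes on to name the active phase and the sustainability effect, so it concerns theta and gamma. The design "evaluation includes a total of 6 sites, where active implementation is initiated in 3 waves each of which includes 2 sites". Section 4.4 handles its own site characteristics in the same way: "these cluster-level characteristics will be included in the GLMM model described above". It presents that work as exploration.

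**The concern.** Calls attended and activities completed do not exist before a site's Kick-Off, and a change in GO score is known only afterwards. If each is one fixed value per site in an additive model, it also predicts encounters from the year before the program. Its coefficient then answers whether sites with a higher value had higher rates on average over all phases. Hypothesis B asks about the rate reached after implementation.

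Two errors could follow. A measure that merely tracks a standing difference between sites could be reported as a benefit of implementation success, and a real effect confined to the later phases would be understated. Separately, three site-level covariates are estimated from six sites, where a normal reference distribution is far too narrow. Hypothesis B is the link between implementation success and quality of care, so a spurious or missed association there would mislead sites that adopt the program.

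**Working it through.** **Inputs from the SAP.** Six sites; three phases including baseline; three site-level covariates; design rates of 25% and 50%; 30, 50 or 70 patients per site; between-hospital CV of 0.2 to 0.8. On the logit scale SD ≈ CV/(1 − p), so at p = 0.25 this range is 0.2/0.75 = 0.27 to 0.8/0.75 = 1.07.

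**Assumptions.** Two-sided alpha of 0.05 (not stated in the SAP), equal phase sizes, and the effect sizes below. None of these effect sizes comes from the SAP.

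**1. The plan's own figure.** The SAP claims: "The six site, stepped wedge design provides >90% power to detect an improvement". This is from 25% to over 50%, and "power was preserved with at least 30 TIA patients per year". With 6 × 30 = 180 patients per period:
- null SE = √(2 × 0.375 × 0.625/180) = 0.0510
- alternative SE = √((0.1875 + 0.25)/180) = 0.0493
- z = (0.25 − 1.96 × 0.0510)/0.0493 = 3.04, so power is 0.999

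Stepped-wedge variance formulas give 0.96-1.00. The claim is reproduced, but it concerns Aim 2. No power or error rate is stated for Hypothesis B.

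**2. What one pooled coefficient estimates.** Each phase contributes roughly in proportion to p(1 − p): 0.1875 at baseline and 0.25 in each later phase. The later phases hold 0.50/0.6875 = 0.727 of the weight, so a post-only effect shrinks by about 27%. For example, 0.60 becomes 0.60 × 0.727 = 0.44.

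**3. Simulation of the estimate.** Logistic model with a random site intercept, three covariates, 50 encounters per site-phase, site SD 0.2, 400 replicates. The phase random effect was omitted because it is confounded with the fixed phase indicators.

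| Truth (log-odds per SD of the measure) | Pooled coefficient | Measure × post-phase term |
|---|---|---|
| 0.60 after, none at baseline | 0.44 | 0.61 |
| 0.40 in every phase (no effect on change) | 0.42, significant in 83% | 0.00, significant in 4% |
| −0.6 at baseline, +0.3 after (change 0.9) | 0.06 | 0.93 |

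A simpler logistic simulation with 40 encounters per site-phase estimated a post-only 0.50 at 0.35, a loss of 30%. The dilution is therefore about 25-30%.

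**4. Residual degrees of freedom.** 6 sites − 1 intercept − 3 covariates = 2. For t with 2 df, P(|t| > c) = 1 − c/√(2 + c²). At c = 1.96 this is 1 − 1.96/√5.8416 = 1 − 0.811 = 0.189. The correct critical value is 4.30. If the between-site variance is estimated by maximum likelihood (divisor 6 instead of 2), c becomes 1.96 × √(2/6) = 1.13 and the size is 0.375.

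**5. Simulated size in the mixed model.** Maximum likelihood, Wald z, no true effect, 600 replicates; Monte Carlo SE at most about 0.02.

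| Encounters per site-phase | Site SD (logit) | Rejection, one given covariate of three | Any of the three |
|---|---|---|---|
| 50 | 0.2 | 0.17 | 0.32 |
| 50 | 0.4 | 0.30 | 0.56 |
| 50 | 0.8 | 0.37 | 0.62 |
| 30 | 0.4 | 0.27 | 0.55 |

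With a single covariate (50 encounters, SD 0.4) the size is still 0.16.

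**6. What the interaction repairs.** It repairs the target of estimation but not the error rate. If sites differ in how much they improve and the model has no site-by-phase random effect, the interaction test rejects a true null about 6.5% of the time at slope SD 0, 11-14% at 0.3 and 24% at 0.5.

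**The case against.** The strongest reply is that the SAP never says the measures are constant over phases. W is indexed by site, phase and encounter, and calls and activities could be coded as zero at baseline, which makes the additive term act like a post-phase term. This reading is possible. In a simulation of that coding (250 replicates, site SD 0.2-0.8), a post-only 0.50 was estimated at 0.51-0.55, against 0.36-0.38 with constant coding. However, it fits poorly with calling the measures cluster-level, and it does not cure the confounding. When a measure tracks only baseline quality (0.40), a bias of 0.10-0.24 remains. An interaction is not excluded either, but none is written.

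Other points limit what can be claimed:
- A reader might infer that the error rate of Aim 3B is wrong as planned. The SAP gives no test, alpha or decision rule for these coefficients, and its normal-theory sentence names other effects. The inflation is therefore conditional on that method being carried over, though no other method is offered.
- A reader might infer that a well-organised site with good baseline care will look successful. The GO measure is a change score on a 1-10 scale, so a site that starts high has less room to rise. Bias from that measure could run the other way.
- The secondary strategy analysis compares percentage change in the rate between sites. That is useful, but it is a different analysis and does not alter the Hypothesis B model.
- Section 4.4 already uses exploratory language and different covariates, so the consequence there is milder.
- The equal-phase assumption is a simplification: the sustainability period runs from 141 days at site F to 416 at site A.

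**Conclusion.** The concern holds as a defect of specification in Aim 3B. On the plain reading, each implementation measure has one coefficient pooled over baseline and later phases. It mixes pre-existing site differences with the post-implementation rate and understates a post-only effect by about 25-30%, given the assumed effects and equal phases. Three covariates on six sites leave 2 df with no small-sample method stated. If normal theory is used for these coefficients, the nominal 5% test has a size of about 19% by the t calculation and 17-37% in simulation, moving towards nominal only as between-site variance nears zero.

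The documents do not support the stronger conclusion that the model cannot address Hypothesis B under any coding. Nor do they support extending the point to the primary Aim 2 comparison, which does not use these measures.

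**What to change.** In Section 4.3, Hypothesis B, state how each measure is coded by phase and choose one of two forms:

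- Replace the pooled main effects with active × measure and sustainability × measure terms, and add a site-by-phase random effect.
- Analyse post-implementation encounters only, adjusted for the site's baseline rate. With all three measures this leaves 6 − 1 − 4 = 1 df (critical value 12.71), so it is practical only with fewer measures.

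Under either form, base inference on the six sites, by permutation over the 6! = 720 orderings or by t with site-level df, and label the result exploratory. Use the same model form for the covariates in Section 4.4.

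Entering one measure at a time is optional. It raises the df to 4 (critical value 2.78) but drops the planned adjustment for call participation.

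The change needs SAP wording and a modified model, with no new data. The cost is wider intervals and little power with six sites.
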